The primary endpoint is to assess the effects of HFNC on maintaining ventilation and oxygenation. This will be ascertained through the need for airway manipulations such as chin lift and jaw thrust to the placement of airway adjuncts such as oral or nasal airways.

In addition, the need for an increased FiO₂ will be recorded. Secondary endpoints will include the lowest and mean pulse oximetry readings, TcCO₂, TcO₂, and the change in these values from the beginning to the end of the procedure. Additional end points will record interruption or aborting of the procedure secondary to difficulties managing the patient's airway. Both groups will be placed on supplemental oxygen via nasal cannula and transported to the recovery room for observation prior to discharge. Pulse oximetry readings will be followed for an hour every 15 minutes after the completion of the procedure in the recovery room to assess for desaturation. Participants will also be evaluated on how they feel prior to discharge.

MATERIALS AND METHODS:

STUDY POPULATION

Participants are eligible for the study if they are greater than 18 years of age and are scheduled for an elective ambulatory upper and/or lower endoscopy under sedation in the gastrointestinal suite at the Moses Campus of the Montefiore

Medical Center. Participants must have a BMI greater than or equal to 40 kg/m².

Inclusion in the study will be voluntary without monetary compensation.

Participants will be excluded if they are less than 18 years of age, pregnant, have severe respiratory failure (hypercapneic and/or hypoxemic), use home oxygen at baseline, have a tracheostomy, or the procedure is an emergency. Patient selection will be obtained by reviewing the GI suite schedule a few days ahead of time screening for patient with a BMI greater than 40.

The patient's chart will then be reviewed during the normal anesthesia pre-operative assessment for criteria that would exclude the patient from the study. If no exclusion criteria are found, the patient will be contacted by phone and the study will be explained and the patient verbally consented. On the day of the procedure or if possible prior to the procedure the patient will sign written consent. The patients will be consented by a member of the study team.

STUDY DESIGN

Eligible patients will be randomized into two groups of thirty patients each¹¹,

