Sample size calculation

Primary objective of this study is to evaluate the effects of HFNC on maintaining ventilation and oxygenation in the two groups. For the purpose of this study if a patient is getting 5 or more air way manipulations such as chin lift and jaw thrust or any other direct interventions to maintain the ventilation and oxygenation will be categorized into the group need for additional support to maintain ventilation and oxygenation. According to our clinical audit when using the standard of care nasal cannula 90% of the patients required additional support for maintaining ventilation and oxygenation. HFNC is now been routinely used in our ORs. We have observed that in majority of the patients when HFNC was used the need for additional airway manipulations were minimal when compared to the regular oxygen cannula. For the purpose of this pilot study sample size calculations are based on the assumptions that 90% of patients using regular cannula will require additional airway manipulations while only 55% in the HFNC group requires the same. Based on a two-sided alpha of 0.05 and Type II error of 20% to achieve a statistically

significant difference between the two groups we need to study 25 patients in each group, a total of 50 patients. Additionally, we plan to increase our sample size by 10% to accommodate for attritions.

Analysis plan

All the analysis will be intention-to-treat analysis. Standard descriptive statistics will be used to explain demographic and clinical characteristics (age, gender, type of surgery, pre-entry medications, ASA status, surgeon, co-morbidities, etc.). The analysis plan assumes that the primary outcome of the trial the proportion of patients requiring addition airway support will be analyzed using the chi-square analysis. Percentage of patients requiring FiO₂ will also be analyzed using chi-square analysis. For all continuous monitoring measurements such as TcCO₂ and TcO₂ the measurements will be averaged for first 5 minutes before the start of any procedure activities and this measurement will serve as the baseline measurement. For all subsequent measurements every 15 minute measurements will be averaged and a delta value will be created comparing it to the baseline. The delta value created will be compared between the two groups.

CONCLUSION:

In the past decade, the obesity epidemic has resulted in a growing need for novel approaches to improve patient safety when receiving anesthesia. First shown

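### TcCO2, TcO2 and the other continuous monitoring measures are compared as an unadjusted change; adjusting for the same baseline costs nothing and may be more precise (minor)

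*Combined protocol and SAP*

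**What the plan says.** The Analysis plan (STATISTICAL ANALYSIS) opens the rule with "For all continuous monitoring measurements such as" and names TcCO2 and TcO2 as examples. The baseline is defined thus: "the measurements will be averaged for first 5 minutes before the start of any procedure activities and this measurement will serve as the baseline measurement". It continues: "For all subsequent measurements every 15 minute measurements will be averaged and a delta value will be created comparing it to the baseline". The comparison itself is one sentence: "The delta value created will be compared between the two groups". The same section names the chi-square test for both binary outcomes, but it names no test, model or covariate for these measures.

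OUTCOMES lists the lowest and mean pulse oximetry, TcCO2 and TcO2 as secondary endpoints, "and the change in these values from the beginning to the end of the procedure". The change therefore extends to oximetry as well as the two transcutaneous measures.

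Two other places bear on the point. RANDOMIZATION has the envelopes opened 30 minutes before the procedure. STUDY DESIGN says that end-tidal CO2 cannot be measured under HFNC flow, so TcCO2 is the only CO2 measurement planned in both arms.

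**The concern.** A longer procedure gives several 15-minute averages and so, on the likelier reading, several deltas. The singular wording also allows just one. The last-window delta would match the beginning-to-end change in OUTCOMES, but the Analysis plan does not make that link. The window to report could then be settled after the data are seen.

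Whichever delta is meant, the baseline is used only by subtraction. That fixes its coefficient at 1 instead of estimating it. Unless 1 happens to be the right slope, some precision is given up in a small trial, although the baseline is already collected.

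**Working it through.** **The plan's own figure.** The only sample size given is for the binary primary outcome: 90% against 55%, two-sided 0.05, 80% power. With pooled variance, n per group = [1.96·√(2·0.725·0.275) + 0.8416·√(0.90·0.10 + 0.55·0.45)]² / 0.35² = 24.3, rounded up to 25. This agrees with the Sample size calculation ("we need to study 25 patients in each group"). It has no bearing on the continuous measures, for which the documents give no figure.

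**Inputs.** From the documents: a 5-minute baseline, 15-minute averages, and 30 per arm ("Eligible patients will be randomized into two groups of thirty patients each"), with 25 per arm as the calculated minimum. Assumed, because the documents are silent: the correlation rho between baseline and follow-up, and k, the follow-up SD divided by the baseline SD.

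**Formulas**, for one follow-up value, in units of the baseline variance:
- change score: 1 + k² − 2·rho·k
- ANCOVA: k²(1 − rho²)
- difference: (1 − rho·k)², which is never negative and is zero when rho·k = 1

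With k = 1 the ratio of ANCOVA to change-score variance reduces to (1 + rho)/2.

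**Example.** For rho = 0.5 and k = 1.25, the change score gives 1 + 1.5625 − 1.25 = 1.3125 and ANCOVA gives 1.5625 × 0.75 = 1.1719. The ratio is 0.89, a gain of 11%.

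**Variance ratio, ANCOVA to change score (reduction in brackets)**

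| rho | k = 1 | k = 1.25 | k = 1.5 |
|---|---|---|---|
| 0.3 | 0.65 (35%) | 0.78 (22%) | 0.87 (13%) |
| 0.5 | 0.75 (25%) | 0.89 (11%) | 0.96 (4%) |
| 0.7 | 0.85 (15%) | 0.98 (2%) | 1.00 (0%) |
| 0.9 | 0.95 (5%) | 0.95 (5%) | 0.78 (22%) |

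A follow-up SD below the baseline SD would give larger gains; it is not tabulated.

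**What the equal-SD column means in practice.** These are detectable differences at 80% power, two-sided 5%, by noncentral t, in SD units, change score then ANCOVA:

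| rho | 30 per arm | 25 per arm |
|---|---|---|
| 0.3 | 0.87, 0.70 | 0.96, 0.77 |
| 0.5 | 0.74, 0.64 | 0.81, 0.70 |
| 0.7 | 0.57, 0.53 | 0.63, 0.58 |
| 0.9 | 0.33, 0.32 | 0.36, 0.35 |

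These hold for k = 1 only. The detectable difference scales roughly with the square root of the variance ratio, so at rho 0.5 and k = 1.5 it falls by only about 2% (√0.964 = 0.98).

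**Small-sample check.** In 20,000 simulated trials per rho, with 30 per arm, equal SDs and correlations, no effect, and 1 to 4 windows per patient unrelated to arm, ANCOVA of the last window kept its type I error at 0.048 to 0.052. Variance ratios were 0.67, 0.76, 0.87 and 0.97, slightly above the formula. The simulation did not include rescue or a procedure length that differs by arm.

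**The case against.** The other side has a good case. OUTCOMES already names a beginning-to-end change, so the contrast is partly supplied. A raw change score is a legitimate analysis in a randomized trial. These are secondary endpoints of a pilot, and the size of the gain rests on assumptions. All of that stands, and it is why the point is minor. What remains is that a comparison of the same data that is at least as precise in large samples is available for nothing.

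Two objections to the remedy also stand, and the fix has to carry them.
- **Timing of the baseline.** It is defined as before procedure activities, not as before the assigned oxygen starts, and allocation is known up to 30 minutes ahead. If the device is already running, the baseline is post-treatment, and neither subtracting it nor adjusting for it is clean.
- **Rescue and early ending.** The last value may follow a face mask or active ventilation. The sample-size assumption (90% against 55% needing additional support of any kind) implies more intervention in controls, which could mask a difference. Procedures may also end early: "Additional end points will record interruption or aborting of the procedure secondary to difficulties managing the patient's airway".

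A reader might infer three stronger things that the documents do not support.
- **That the change score is biased.** It is not, given randomization and a pre-device baseline.
- **That the plan inflates false positives.** If every window were tested at 0.05, the chance of at least one false positive per measure would be about 9%, 13% or 16% for 2, 3 or 4 windows at a delta correlation of 0.5, and 8%, 10% or 11% at 0.8. The plan does not say that each window is tested, and with one window there is no excess.
- **That a gain of 25% or 35% can be counted on.** Those figures need equal SDs before the procedure and under sedation, which nothing in the documents establishes.

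**Conclusion.** The point holds as a minor improvement, not as the correction of an error. The planned comparison uses baseline by subtraction only and is not linked to the change listed in OUTCOMES. Adjusting for the same baseline is at least as precise in large samples. Over the values tried (rho 0.3 to 0.9, follow-up SD 1 to 1.5 times baseline) the reduction in variance runs from nil to about a third. All of these values are assumptions. Validity of either analysis depends on a pre-device baseline, which the documents do not state. The lowest and mean oximetry endpoints are unaffected, as are the primary chi-square analysis and the sample size.

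**What to change.** In the Analysis plan, replace the comparison of deltas with one prespecified analysis per measure: ANCOVA of the last available 15-minute average, with arm and the 5-minute baseline as covariates. With baseline in the model, the arm effect is the same whether the outcome is the last value or its change, so this is the beginning-to-end change in OUTCOMES and needs no new endpoint. Say how a part-filled last window is averaged, for instance over the time recorded. Report the other windows descriptively.

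State that the 5-minute baseline is recorded before the assigned oxygen device starts.

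State as limitations that the last value may follow rescue oxygen or ventilation, expected more often in controls, and that procedures may end early; adjustment removes neither. Report by arm the number of windows and the number of patients rescued before the last window.

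The cost is a few sentences of text and slightly more analysis work, with no extra patients and no added measurements. If the device is at present started before those five minutes, the baseline recording would need to come earlier.
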